#### 5. Follow-up of discontinued patients

Subjects who receive study drug and are discontinued from the study will have all safety assessments completed, including a complete physical examination and laboratory evaluation including chemistry, hematology with differential, urinalysis and urine pregnancy test as required at study termination. This testing should be done as soon as possible. Medical follow-up of any severe adverse events or clinically significant abnormal laboratory values will continue until the abnormality resolves, and adequate medical explanation is apparent.

Such data will be provided to Sunovion.

## **X. STATISTICAL EVALUATION**

### **A. Sample Size**

Estimations based on an overall composite score (sustained attention and memory [SAM] + neuropsychological) for carbamazepine-levetiracetam (Meador et al, 2007) would predict that with a sample size of 30 subjects in a 2-period crossover study, the probability is 90% that the study will detect a treatment difference at a 2-sided 0.01 significance level, if the true difference between the treatments is 0.370 units. This is based on the assumption that the SD of the difference in the response variables is 0.490. Given an estimated dropout of 30% to 40%, the planned sample size needed to enroll is 40 to 45 subjects.

The SDMT is a neuropsychological measure that has been sensitive to AED effects in multiple studies. Based on the SDMT for carbamazepine vs. nondrug in the carbamazepine-levetiracetam study, a total of 31 subjects will need to complete the 2-period crossover study. The probability is 90% that the study will detect a treatment difference at a 2-sided 0.01 significance level, if the true difference between the treatments is 3.800 units. This is based on the assumption that the standard deviation of the difference in the response variables is 5.100. Given an estimated dropout of 30% to 40%, the study would need to enroll between 42 and 47 subjects.

Based on the above 2 scenarios, the planned sample size to enroll in this study is 46 subjects to complete 30.

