### **BRIEF DESCRIPTION OF STUDY**

This study is a double-blind, randomized, two period crossover design. The study consists of 6 visits over a 21 week period. Fifty (50) normal healthy subjects will be treated with both Eslicarbazepine acetate (ESL, 800 mg/day) and Carbamazepine (CBZ, 800mg/day) for 6 weeks and 3 days each (maintenance 4 weeks and taper 3 days). Each antiepileptic drug (AED) treatment period will be followed by a four day taper and washout period off AED for the remainder of the month. Cognitive and behavioral function testing along with safety testing will be conducted at pretreatment baseline, the end of each randomization AED maintenance period, and after the final washout period.

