### **TIME PERIOD AND NUMBER OF SUBJECTS**

A. Anticipated Number of Subjects: 50 (to obtain 30 evaluable subjects)  
B. Anticipated Duration of Study: 1 Year

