## **V. STUDY POPULATION**

### **A. Number and type of subjects**

Healthy males and females between the ages of 18 and 55 who do not require concomitant medications that affect study medications or cognitive and behavioral functions. Fifty subjects will be enrolled in the study in order to complete 30 subjects.

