**D. Enrollment Goals**

Previous studies indicate that an enrollment of 46 subjects will be required to obtain 30 evaluable subjects. See Statistical Section for power analysis.

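### The enrolment ranges in X.A do not follow from the stated 30–40% dropout (they fit 25–33%), and planned enrolment is 46 in two places and 50 in three

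*Combined protocol and SAP*

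**What the plan says.** Section X.A sizes the trial in two ways, each for 90% power at a two-sided 0.01 level.

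- **Composite score:** 30 completers, then "Given an estimated dropout of 30% to 40%, the planned sample size needed to enroll is 40 to 45 subjects".
- **SDMT:** "a total of 31 subjects will need to complete the 2-period crossover study". At the same 30–40% dropout, "the study would need to enroll between 42 and 47 subjects".

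X.A concludes that "the planned sample size to enroll in this study is 46 subjects to complete 30". Section VI.D agrees: "an enrollment of 46 subjects will be required to obtain 30 evaluable subjects".

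Three other places give 50:

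- Brief Description of Study: "Fifty (50) normal healthy subjects will be treated with both" drugs.
- Time Period and Number of Subjects: "50 (to obtain 30 evaluable subjects".
- Section V.A: "Fifty subjects will be enrolled in the study in order to complete 30 subjects".

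Section IX.E says that subjects who drop out before finishing cognitive testing are not replaced.

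**The concern.** Inflating 30 completers for 40% loss gives 50, yet X.A prints 45 as its upper limit. The SDMT sentence has a gap of the same size, so a single mistyped digit does not explain it. The figure of 46 is then drawn from these ranges, while other sections give 50.

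The 90% power claim is tied to 30 or 31 completers with almost no slack, and dropouts are not replaced. The number enrolled is therefore the main protection against attrition. As written, a reader cannot tell which dropout assumption or which enrolment number the power claim rests on.

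**Working it through.** **Inputs, all from X.A.** Two-sided alpha 0.01 and power 90%. Composite: difference 0.370, SD of the difference 0.490, 30 completers. SDMT: difference 3.800, SD 5.100, 31 completers. Dropout 30% to 40%.

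**Step 1: the completer targets reproduce.** Paired t-test, noncentral t with n − 1 degrees of freedom and noncentrality (difference/SD)·√n:

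| Completers | Composite power | SDMT power |
|---|---|---|
| 27 | 0.863 | 0.852 |
| 28 | 0.879 | 0.869 |
| 29 | 0.894 | 0.884 |
| 30 | 0.906 | 0.898 |
| 31 | 0.918 | 0.910 |

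The smallest n reaching 90% is 30 for the composite and 31 for SDMT, as stated. With n − 2 degrees of freedom the answers are the same.

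**Step 2: the enrolment ranges do not reproduce.** Enrolled = completers/(1 − dropout), rounded up:

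| Completers | At 30% | At 40% | Printed |
|---|---|---|---|
| 30 | 30/0.70 = 42.9 → 43 | 30/0.60 = 50 | 40 to 45 |
| 31 | 31/0.70 = 44.3 → 45 | 31/0.60 = 51.7 → 52 | 42 to 47 |

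The printed limits are low by 3 at the lower end and 5 at the upper end. The cruder formula completers × (1 + dropout) does not return them either. It gives 39 to 42 for 30 completers and 41 to 44 for 31.

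**Step 3: which dropout gives the printed ranges?**

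- At 25%: 30/0.75 = 40; 31/0.75 = 41.3 → 42.
- At one third: 30/(2/3) = 45; 31/(2/3) = 46.5 → 47.

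All four limits are matched exactly.

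**Step 4: the dropout that 46 and 50 can absorb in expectation.**

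- 46 enrolled: 1 − 30/46 = 34.8% for 30 completers; 1 − 31/46 = 32.6% for 31.
- 50 enrolled: 1 − 30/50 = 40.0% for 30 completers; 1 − 31/50 = 38.0% for 31.

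**Step 5: effect on power.** The number of completers is taken as Binomial(enrolled, 1 − dropout), and the power from Step 1 is averaged over it:

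| Enrolled | Dropout | Expected completers | P(at least 30) | Composite power | SDMT power |
|---|---|---|---|---|---|
| 46 | 25% | 34.5 | 0.95 | 0.945 | 0.939 |
| 46 | 30% | 32.2 | 0.81 | 0.925 | 0.917 |
| 46 | 33.3% | 30.7 | 0.65 | 0.907 | 0.899 |
| 46 | 35% | 29.9 | 0.56 | 0.898 | 0.889 |
| 46 | 40% | 27.6 | 0.29 | 0.863 | 0.853 |
| 50 | 30% | 35.0 | 0.95 | 0.948 | 0.942 |
| 50 | 40% | 30.0 | 0.56 | 0.898 | 0.889 |

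At 40% dropout the choice between 46 and 50 is worth about 3.5 percentage points of power.

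**The case against.** The arithmetic is not in dispute. The case for treating the point as minor runs as follows.

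- **Fifty is already in the protocol.** It equals 30/0.60, the enrolment needed at the worst stated dropout. If 50 governs, only the printed ranges and the two mentions of 46 are wrong. That is fair, but nothing says 50 governs, and the section that justifies the sample size says 46.
- **The power loss depends on alpha 0.01.** Section X.B names no significance level for the primary test. If 0.05 were assumed, 46 enrolled at 40% dropout would still give average power of about 0.96 on both measures. This stands as a limit on the practical harm. However, 0.01 is the only level in the documents and the one to which the 90% claim is attached.
- **The ranges are the likelier slip.** The 30–40% rate is stated twice, and 46 and 50 taken to 30 imply 34.8% and 40.0%, both inside that range. This is suggestive but not conclusive, because 46 also lies between the printed upper limits of 45 and 47. It does mean that lowering the dropout rate would need its own justification.
- **The target is worded differently in places.** The Brief Description gives 50 without a target, and some sections say evaluable where others say complete. The Time Period section and V.A both tie 50 to 30, so the conflict remains.
- **Some subjects are replaced.** Section IX.B replaces those excluded for the HLA allele. They never receive drug, so this does not offset dropout on treatment.

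**Conclusion.** Both parts hold. The enrolment ranges in X.A are inconsistent with the dropout rate stated in the same sentences, and the protocol carries two enrolment numbers that rest on different dropout assumptions. The completer targets of 30 and 31 are sound.

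The consequence is modest and conditional. Forty-six is adequate at 30% dropout, and at 25–33% it gives composite power of 0.907–0.945 and SDMT power of 0.899–0.939. It falls short in the upper part of the stated range, by about 4 points (composite) and 5 points (SDMT) below 90% at 40%. Fifty is itself only just at that level there. These figures assume the effect sizes and SDs in X.A, two-sided alpha 0.01, and independent dropout at a common rate. This is a planning inconsistency that biases no estimate, but it should be corrected because it concerns the number supporting the power claim.

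**What to change.** 1. In X.A, make the dropout rate and the ranges agree. Either keep 30–40% and change the ranges to 43–50 (30 completers) and 45–52 (31 completers), or keep 40–45 and 42–47 and change the dropout rate to about 25–33%. The second choice needs a stated justification, since no section gives that rate.
2. Use one enrolment number throughout.
   - If 50: change X.A and VI.D, and note that at 40% dropout it gives 30 expected completers and average power of about 90% (composite) and 89% (SDMT).
   - If 46: change the Brief Description, the Time Period section and V.A. State that it supports 30 completers only up to about 35% dropout and gives about 86% (composite) and 85% (SDMT) power at 40%.

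The cost is a text correction: four range limits or one percentage range in two sentences, plus the enrolment number in two or three places. No recruitment beyond the 50 already stated is needed.

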#### D. Definition of Evaluable Subjects

Any subject who ingested one or more doses of blinded study medication and provided follow-up information will be evaluable for the analysis of the safety data. The primary analysis will include subjects who complete all visits for the primary variable in both periods and who did not have any important deviations, which may have an impact on cognitive function. Subjects who prematurely discontinue the study will be evaluated based on the data collected at each visit attended. Any subject who is evaluable for the safety analysis who also has baseline and end of drug period cognitive/behavioral data available for each of the two drug periods will be evaluable for the intent-to-treat analysis of the parameters of interest. Any subject evaluable for the intent-to-treat analysis will be evaluable for the per-protocol analysis of the parameters of interest provided that the subject was compliant with the protocol with regard to the study medication regimen, use of concomitant medications, sleep requirements prior to cognitive testing, alcohol consumption, caffeine consumption, and use of OTC medications prior to cognitive testing. All data will be used to their maximum possible extent, but without any imputations for missing data for any parameter.

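### With 46 enrolled, the plan's own dropout range does not reliably give the 30 analysed pairs its 90% power needs, and the 30 is never tied to the primary analysis set

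*Combined protocol and SAP*

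**What the plan says.** Section X.A (Sample Size) makes two calculations. For the overall composite, 30 subjects are said to give 90% power to "detect a treatment difference at a 2-sided 0.01 significance level, if the true difference between the treatments is 0.370 units", on the assumption that "the SD of the difference in the response variables is 0.490". For the SDMT, with a difference of 3.8 and an SD of 5.1 at the same level and power, it says that "a total of 31 subjects will need to complete the 2-period crossover study". Both are inflated for an estimated 30% to 40% dropout, to 40–45 and 42–47 enrolled. No other loss is named. X.A then draws the two together: "the planned sample size to enroll in this study is 46 subjects to complete 30".

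Elsewhere the target is described differently:

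- VI.D (Enrollment Goals): "an enrollment of 46 subjects will be required to obtain 30 evaluable subjects".
- Time Period and Number of Subjects (front matter): 50, for 30 evaluable.
- V.A (Number and type of subjects): 50, for 30 completers.
- Brief Description of Study: 50, with no target.

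X.D (Definition of Evaluable Subjects) restricts the primary analysis to subjects who finish the visits for the primary variable in both periods and "who did not have any important deviations, which may have an impact on cognitive function". It also defines a safety set, an intent-to-treat set and a per-protocol set, and rules out imputation. IX.E says that subjects who drop out before finishing cognitive testing are not replaced.

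**The concern.** The power statement applies to the number of within-subject differences that enter the primary analysis. The plan uses 30 for completers in one place and for evaluable subjects in another, and its primary set is a subset of completers. A reader therefore cannot tell which count the 90% belongs to, or whether 46 or 50 is meant to deliver it. Dropouts are not replaced and nothing is imputed, so no later step restores lost pairs. What is at stake is whether the design has the power it claims for its single primary comparison.

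**Working it through.** **Inputs.** All are from X.A: two-sided alpha 0.01; composite difference 0.370, SD of the difference 0.490; SDMT difference 3.8, SD 5.1; dropout 30% to 40%. Enrolment is 46 (X.A, VI.D) or 50 (front matter, V.A). The share of completers excluded for deviations is not given in the documents. Where it is used below it is an assumption.

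**Formula.** Paired t-test on n within-subject differences. Noncentrality = (difference / SD) × √n, df = n − 1, and power = the probability that a noncentral t exceeds the two-sided 0.01 critical value in absolute size.

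**Step 1: reproduce the plan's figures.** For the composite, 0.370 / 0.490 = 0.755, and at n = 30 the noncentrality is 0.755 × √30 = 4.14.

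| Pairs analysed | Composite power |
|---|---|
| 35 | 95.2% |
| 32 | 92.8% |
| 31 | 91.8% |
| 30 | 90.6% |
| 29 | 89.4% |
| 28 | 87.9% |
| 27 | 86.3% |
| 25 | 82.5% |
| 24 | 80.3% |

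The stated 30 is reproduced and is the smallest n at or above 90%. With df = n − 2, to allow for a period term, power at 30 is 90.5% and the minimum is still 30. For the SDMT, power is 91.0% at 31 and 89.8% at 30, so the stated 31 is also reproduced as the minimum.

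**Step 2: apply the plan's dropout range, with no exclusions.**

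| Enrolled | Dropout | Completers | Composite power |
|---|---|---|---|
| 46 | 30% | 46 × 0.70 = 32.2 | about 93% (n = 32) |
| 46 | 40% | 46 × 0.60 = 27.6 | 86.3% to 87.9% (n = 27 or 28) |
| 50 | 30% | 50 × 0.70 = 35 | 95.2% |
| 50 | 40% | 50 × 0.60 = 30 | 90.6% |

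Going from 46 to 30 is a loss of 16 / 46 = 34.8%. Any dropout above that leaves fewer than 30 completers. The inflation in X.A explains the gap: 30 / (1 − 0.30) = 42.9 and 30 / (1 − 0.40) = 50, so 30 completers need 43 to 50 enrolled, against the 40 to 45 stated.

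**Step 3: add exclusions.** With exactly 30 completers, one exclusion gives 89.4%, two give 87.9% and three give 86.3%. With 46 enrolled and 30% dropout, two of the 32 completers can be excluded and 30 remain. With 50 enrolled, five can be excluded at 30% dropout and none at 40%.

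As an illustration only, excluding an assumed 5%, 10% or 20% of 30 completers leaves 28.5, 27 or 24. Rounded down, power is 87.9%, 86.3% or 80.3%. With 46 enrolled, 40% dropout and an assumed 10% excluded, 46 × 0.60 × 0.90 = 24.8, or 80.3% to 82.5% at 24 or 25.

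**The case against.** A reader might infer that the 90% power holds only if no completer is ever excluded. The plan's figures do not support that. It is true at exactly 30 completers, but at 30% dropout 46 enrolled leave room for two exclusions, and 50 leave room for five.

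A reader might also infer that X.A and VI.D flatly contradict each other. They need not. X.D uses the word evaluable for several sets, and its intent-to-treat set requires baseline and end-of-period data for both drugs but no freedom from deviations. On that reading, 30 evaluable and 30 completing nearly coincide. What remains is an undefined term, and that reading still leaves the primary set potentially smaller.

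Nor do the documents show that completers will be excluded. The detailed conditions on sleep, alcohol, caffeine and over-the-counter drugs belong to the per-protocol set. The primary set removes only important deviations, which X.D does not list. Testing is rescheduled after breaches involving alcohol or non-approved drugs (VI.E, Visits 3 and 5) or sleep, medication or caffeine (IX.A). Repeated noncompliance is cause for removal (IX.D), so some of those subjects would already count as dropouts. These points should keep exclusions few, and one exclusion costs only about one point of power. They do not affect the loss from dropout alone.

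The SDMT shortfall is trivial: 89.8% rounds to 90%, and individual tests are secondary under X.B.

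**Conclusion.** The point holds as a matter of size and definition. With 46 enrolled, composite power runs from about 93% down to 86–88% over the plan's own dropout range before any exclusion, and is below 90% once fewer than 30 complete. With 50 enrolled it runs from about 95% to 90.6%, with nothing to spare at 40% dropout. At exactly 30 completers, any exclusion takes power below 90%. Dropout is the larger risk; exclusions add an amount that the documents do not let anyone estimate.

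These figures rest on the plan's difference, SD and alpha and on a paired t-test. The 5% to 20% exclusion figures are illustrations, not predictions. The documents do not support concluding that the trial is seriously underpowered or that enrolment must rise. The 31-versus-30 discrepancy for the SDMT is a minor inconsistency.

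**What to change.** Revise X.A, and align VI.D, V.A and the front matter with it:

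1. State that the 30 behind the power claim means subjects in the X.D primary analysis set.
2. Reconcile 46 with 50 and use one enrolment figure throughout.
3. Give the expected size of the primary set over 30% to 40% dropout: about 32 down to 27 or 28 from 46, or 35 down to 30 from 50, before exclusions. If an allowance for exclusions is added, label it an assumption.
4. Replace the flat 90% with the power range at those sizes, and keep 90.6% as the figure that applies if 30 are analysed.
5. State SDMT power as 89.8% at 30, or remove the implication that 30 meets a requirement of 31.

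The cost is wording only. No increase in enrolment is required, since the choice is between two numbers already in the plan. The stated power becomes slightly less favourable.

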### **B. Methodology for statistical analysis**

The parameters of interest are listed in Section VII. Descriptive statistics will be used to provide an overview of the primary, secondary, and other variable results. For categorical parameters, the number and percentage of subjects in each category will be presented. The denominator for percentages will be based on the number of subjects appropriate for the purpose of analysis. For continuous parameters, descriptive statistics will include number of subjects, mean, standard deviation (SD), median, minimum, and maximum. Unless otherwise specified, baseline neuropsychological data will be based on the Visit 2 assessments.

The primary outcome (pharmacodynamic) variable will be analyzed as the within subject difference between drugs in the overall neuropsychological composite Z-score for CBZ vs. ESL comparing between end of Maintenance Period scores for each drug (ie, Treatment Period 1 to Treatment Period 2). The overall composite Z-score will be computed for each condition from the individual cognitive test scores from the computerized tests and non-computerized neuropsychological tests (including the behavioral questionnaires) after transformation to Z-scores. The Z-score will be calculated using the values (mean and SD) from the average of the scores from the 3 nondrug conditions (Baseline, first Washout Period, and second Washout Period).

The primary analysis will compare the composite Z scores for ESL to Carbamazepine

for each subject at the end of the Treatment Maintenance Periods. Since the analysis is based on an overall composite score, no correction for multiple comparisons is necessary. The use of composite Z-scores avoids Type II error.

Secondary analyses will be conducted to compare the two AEDs states to the non-drug average from Visits 2, 4 & 6. The initial cognitive assessment (i.e., Visit #1) is given to reduce practice effects and will not be used in the statistical analyses. Secondary analyses will also be conducted comparing the 2 drug states to each other and the non-drug state for the individual neuropsychological variables.

Summary statistics will be calculated by treatment for each evaluation of antiepileptic blood levels (ABLs). Additional analyses of data will be performed which take the ABLs into account. Linear correlations of plasma concentrations and the overall composite and individual score variables will be plotted with a fitted regression line superimposed for each drug condition.

The incidences of all adverse events reported during the trial will be tabulated by treatment and study period. The other safety variables, which include changes in hematology, clinical chemistry, and urinalysis parameters, and vital signs will be analyzed descriptively. The actual measurement and its change from Baseline will be presented by visit and period of collection. In addition, shift tables may be used to evaluate the number and percentage of subjects having a different post-Baseline status when compared with their Baseline status.

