**Study weeks 6 - 10**

The subject will be tapered off drug over the first 3 days and then remain off drug for the next 25 days.

**Visit 4**      (Study week 10)

This visit ends the washout period and begins the baseline for Drug Period 2. At this visit, vital signs and a brief physical examination will be obtained. Subjects will undergo cognitive and behavioral testing and then the alternate drug treatment will be dispensed. Titration will be similar to the first titrations beginning at Visit 2. In addition, a pregnancy test will be obtained in women of child bearing potential.

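### The primary contrast has no period or sequence term, so drift between periods stays in the error and can bias the ESL-CBZ difference; the period baselines are also unused, but their value is uncertain

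*Combined protocol and SAP*

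**What the plan says.** **Primary contrast (X.B).** "The primary analysis will compare the composite Z scores for ESL to Carbamazepine" at the end of the maintenance periods, as a within-subject difference. The section names no test or model, and no term for period, sequence or baseline.

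**Baseline (X.B).** Unless otherwise specified, "baseline neuropsychological data will be based on the Visit 2 assessments". The sentence closes the paragraph on descriptive statistics. Visit 4 is used elsewhere in X.B: it is one of the three nondrug conditions behind the Z-score mean and SD, and it is part of the nondrug average of Visits 2, 4 and 6 in the secondary analyses.

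**Testing schedule (VI.E, IX.A).** The battery is given at Visit 2 before the first dose and at Visit 4 before the second drug is dispensed. Of Visit 4, VI.E says: "This visit ends the washout period and begins the baseline for Drug Period 2". The visits that matter here fall at weeks 0, 6, 10 and 16.

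**Evaluability (X.D).** The intent-to-treat set needs baseline and end-of-period cognitive data for each of the two drug periods.

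**Sample size (X.A).** With 30 completers the study has 90% power to "detect a treatment difference at a 2-sided 0.01 significance level, if the true difference between the treatments is 0.370 units". The variability input is stated as follows: "This is based on the assumption that the SD of the difference in the response variables is 0.490".

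**The concern.** Repeated cognitive testing tends to drift with practice. The Visit 1 session is meant to reduce this, but nothing in the plan says that it removes it. Visits 3 and 5 are ten weeks apart, with a further test session between them. A shift common to all subjects enters the ESL minus CBZ difference with opposite signs in the two sequences. If the sequences are equal in size, the shift cancels from the mean but inflates the variance. If they are unequal, it also biases the estimate. Inequality is plausible: X.A expects 30-40% dropout, X.D restricts the primary analysis to completers, and X.E-type imputation is ruled out because X.D allows none. VI.E says only that the order is random.

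Subject-specific drift is a separate matter. X.D treats each period as having its own baseline, yet the primary contrast uses neither. Because X.B names no model, an analyst could also choose between adjusted and unadjusted results after seeing the data.

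**Working it through.** **1. Reproduce the plan's figure.** Inputs from X.A: difference 0.370, SD of the difference 0.490, two-sided alpha 0.01, n = 30. For a paired t-test the noncentrality is 0.370/0.490 × √30 = 4.14 on 29 df, which gives 90.6% power; 30 is the smallest n that reaches 90%. The SDMT inputs (3.800, 5.100) likewise give 31, with 91.0% power. The normal approximation gives 27 in both cases. The stated figures therefore match an unadjusted paired t-test.

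**2. The model with a sequence term.** Let τ be ESL minus CBZ, π the period shift, and D the period 2 minus period 1 composite. Assuming no differential carryover:
- ESL first: E(D) = π − τ
- CBZ first: E(D) = π + τ

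Half the difference between the sequence means of D is τ, free of π. With 15 subjects per sequence the standard error is the same as in step 1, on 28 df. Power is 90.5%, so the term costs about 0.15 point.

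**3. What omitting the term costs.** In a bare paired analysis with equal sequences, the variance of the difference rises to about 0.490² + π². The documents give no π, so these values are assumptions.

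| π (assumed) | Inflated SD | Paired power | With sequence term |
|---|---|---|---|
| 0 | 0.490 | 90.6% | 90.5% |
| 0.1 | 0.500 | 89.3% | 90.5% |
| 0.2 | 0.529 | 84.9% | 90.5% |
| 0.3 | 0.575 | 77.3% | 90.5% |

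The paired column treats the shift as normal noise. Simulating it as a fixed ±π with 15 subjects per sequence (200,000 trials) gives 89.7%, 86.5% and 80.3% for the last three rows. Hence about 85-87% at π = 0.2.

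**4. Bias with unequal sequences.** The bias of the unadjusted mean is π(n₁ − n₂)/n in size. With π = 0.2 and an 18/12 split (both assumed) it is 0.2 × 6/30 = 0.04, or 11% of 0.370. The sequence term removes it. The standard error then becomes (0.490/2) × √(1/18 + 1/12) = 0.0913, against 0.0895 at 15/15, and power is 89.1%.

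**5. The baseline-difference covariate.** Write c(k) for the correlation between scores k weeks apart. At weeks 0, 6, 10 and 16, the correlation of (V5 − V3) with (V4 − V2) is

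r = [2c(6) − c(16) − c(4)] / [2(1 − c(10))].

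If all visits correlate equally, r = 0. Otherwise assume exponential decay with correlation 0.6-0.9 per average gap (16/3 = 5.33 weeks). At 0.8: c(4) = 0.846, c(6) = 0.778, c(10) = 0.658 and c(16) = 0.512. So r = (1.556 − 0.512 − 0.846)/0.684 = 0.29 and R² = 0.084. Over 0.6-0.9, R² runs from 0.03 to 0.12. If 10-30% of the variance is occasion-specific noise (assumed), R² falls to about 0.01-0.05.

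Power uses SD 0.490 × √(1 − R²), 27 df, and a variance factor of 27/26 for estimating the slope:
- R² = 0: 89.0%
- R² = 0.04: 90.4%, about break-even against 90.5%
- R² = 0.12: 93.0%

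The covariate is thus worth −1.5 to +2.5 points.

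**6. Simple change from period baseline.** With equal variances the SD is 0.490 × √(2 − 2r). This gives power of 57.2% at r = 0, 72.8% at r = 0.25 and 90.6% at r = 0.5. It is worse than the plan whenever r is below 0.5.

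**The case against.** The planned power is reached without any covariate, and the crossover already removes stable differences between subjects. The practice session at Visit 1 and the random order limit average drift, and X.B may intend a period term without saying so. All of this stands. It makes the point an improvement, not an error in the stated power. It does not supply the missing model, and random order does not guarantee equal sequences among completers.

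A reader might infer that the plan fixes baseline at Visit 2 for everything and loses precision as a result. The documents do not support that. The Visit 2 sentence is a default with an exception clause, Visit 4 enters the Z-score reference and the nondrug average, and the primary contrast uses no baseline at all. A single Visit 2 value, or a common nondrug reference, is the same for both periods and cancels.

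A reader might also expect the baseline covariate to cut variance by 9-20%. That range follows from equally spaced visits with no occasion noise. The actual gaps are 6, 4 and 6 weeks, so Visit 3 lies closer to the other period's baseline than to its own. The documents report no correlations, so even the sign of the gain is open. The covariate also relies on negligible residual drug effect at Visit 4, an assumption the plan already makes by counting that visit as nondrug.

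**Conclusion.** The point holds as a cheap improvement. The primary contrast as written leaves average drift between periods in the error term and exposed to bias when the sequences are unequal. At the plan's 0.370, an assumed shift of 0.2 costs about 4 to 6 points of power, and with an 18/12 split it biases the estimate by 0.04 units. With no shift, the sequence term costs about 0.15 point. The size rests on an assumed shift and split, and on no differential carryover. The baseline covariate is an option whose benefit is not established.

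**What to change.** In X.B:
- State the primary model as the period 2 minus period 1 composite difference with a sequence term, and report half the difference between sequences as the period-adjusted ESL minus CBZ effect.
- Pre-specify one supporting analysis that adds the Visit 4 minus Visit 2 composite difference as covariate, without presenting it as a sure gain.
- Say that Visit 4 is the baseline for Period 2 wherever a period baseline is used, so that X.B agrees with VI.E and X.D.
- Do not use simple change scores for the drug contrast.

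The cost is SAP wording and one degree of freedom in the primary model. No extra data are needed.

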## **III. STUDY OBJECTIVE**

The objective of this study is to determine whether there are any differences in the cognitive abilities and/or behavioral response of normal healthy volunteers after 6 weeks of treatment with ESL compared to Carbamazepine.

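### Section X.B says that composite Z-scores avoid Type II error; by the plan's own sizing the composite test has a Type II error of about 9% to 10% at 0.37 units, 28% at 0.30 and 48% at 0.25

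*Combined protocol and SAP*

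**What the plan says.** Section X.B makes the within-subject difference between the drugs in an overall composite Z-score the only primary outcome. It argues that one composite needs no multiplicity correction, and then adds: "The use of composite Z-scores avoids Type II error".

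Section X.A sizes the trial on a composite. Its statement reads: "with a sample size of 30 subjects in a 2-period crossover study, the probability is 90% that the study will detect a treatment difference". The alpha is two-sided 0.01, and the condition is: "if the true difference between the treatments is 0.370 units". The variability is given as follows: "This is based on the assumption that the SD of the difference in the response variables is 0.490". Both figures come from another study and another composite: "Estimations based on an overall composite score (sustained attention and memory [SAM] + neuropsychological) for carbamazepine-levetiracetam".

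The objective in Section III is to "determine whether there are any differences in the cognitive abilities and/or behavioral response of normal healthy volunteers".

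For continuous variables X.B lists number of subjects, mean, SD, median, minimum and maximum. It names no confidence interval for the primary difference and states no alpha for the primary test. It does plan secondary comparisons of the two drugs on each individual neuropsychological variable.

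**The concern.** No test with finite power avoids Type II error, and X.A puts a number on the error that this trial accepts. The two sections therefore disagree about the same primary test.

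The sentence matters most if the composite result is nonsignificant. The trial looks for any difference between two drugs, with 30 completers and a strict significance level. If the plan has said in advance that false negatives are avoided, a null result is easily taken to mean that the drugs are alike. Without a planned interval, the primary result does not show which differences the data exclude.

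The sentence also passes over a known weakness of composites. An effect on one or a few functions is averaged with tests that do not move, so for effects of that kind a composite can raise the Type II error.

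**Working it through.** **Inputs.** From X.A: n = 30 completers, SD of the within-subject difference 0.490, difference 0.370, two-sided alpha 0.01. For the SDMT alone: difference 3.800, SD 5.100, n = 31. X.B states no alpha, so 0.01 is taken from the sizing.

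**Formula.** Noncentral t test on the within-subject difference, with ncp = (difference / SD) × √n. I used df = n − 1 (paired); df = n − 2 (crossover) changes the results only slightly.

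**Step 1: reproduce the plan's figures.** For the composite, ncp = 0.370/0.490 × √30 = 4.14. Power is 90.6% with df 29 and 90.5% with df 28, and 30 is the smallest n that reaches 90%. For the SDMT at n = 31, power is 91.0% (df 30). Both sizing statements reproduce.

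**Step 2: Type II error of the composite test** (n = 30, SD 0.490, two-sided 0.01):

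| True difference | ncp | Type II error |
|---|---|---|
| 0.37 | 4.14 | 9% to 10% |
| 0.30 | 3.35 | 28% |
| 0.25 | 2.79 | 48% |
| 0.20 | 2.24 | 68% |

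If the primary test were run at 0.05, the error would be 2% at 0.37, 10% at 0.30 and 23% at 0.25. It is smaller, but not zero.

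**Step 3: dilution of a focal effect.** Section VII lists 8 computerized and 4 non-computerized tests that feed the composite. Symbol digit coding has two measures marked for a Z-score, so a literal count is 13. *Assuming* equal weights, which X.B does not state, an effect f on one of 12 tests becomes f/12. For f = 1.0 Z the composite moves by 1.0/12 = 0.083. The share of trials in which the primary test misses it is then:

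| Composite SD of difference | alpha 0.01 | alpha 0.05 |
|---|---|---|
| 0.490 (X.A) | 96% | 85% |
| 0.25 (assumed) | 80% | 58% |
| 0.20 (assumed) | 67% | 40% |

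The direction is clear. The size is not fixed by the documents.

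**Step 4: what an interval would show.** SE = 0.490/√30 = 0.0895. The half-width is 2.045 × 0.0895 = 0.18 at 95% and 2.756 × 0.0895 = 0.25 at 99%.

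**The case against.** The best defence is context. The preceding sentence in X.B concerns multiplicity, so the authors probably meant that one composite avoids the power lost by correcting many tests. That advantage is real. A 3.8-unit SDMT effect (SD 5.1, n = 30) has 90% power at 0.01, and about 64% after a Bonferroni correction for 12 tests (0.01/12). This supports a statement that a composite *may reduce* Type II error for effects shared across tests. It does not support *avoids*. The 90% power in X.A does not cure the sentence either, because it contradicts it.

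The defence is right on three further points.

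- A reader might infer that the design is almost certain to miss a focal effect. The documents do not support that. Step 3 needs equal weights, an SD borrowed from a different composite, an alpha that X.B does not state, and movement on one test only. The battery also holds two closely similar coding tasks (the SDMT and symbol digit coding), so a coding-speed effect would probably not stop at one score.
- A reader might infer that nothing in the plan offsets the sentence. X.B already plans drug-to-drug comparisons on the individual variables, and the SDMT alone has about 90% power for 3.8 units. These comparisons are secondary, have no stated multiplicity control, and the 3.8 units are for carbamazepine against nondrug, so the cover is partial.
- The plan sets no equivalence margin and no rule for reading a null result. Misreading is a risk that the sentence invites, not something that the plan prescribes.

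**Conclusion.** The sentence is wrong and should not stand. By the plan's own sizing, the composite test has a Type II error of 9% to 10% at 0.37, 28% at 0.30 and 48% at 0.25. These figures assume 30 completers, an SD of 0.490 carried over from another composite, and a primary test at two-sided 0.01.

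A composite helps when an effect is shared across tests and loses power when it is limited to a few. The documents do not fix how large that loss would be, and the secondary per-test comparisons partly cover it. The defect lies in a stated property of the primary test and in the lack of a named interval. The primary comparison and the sample size calculation are not invalidated by it. It should be corrected because it bears on what a null result can be said to show.

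**What to change.** In X.B, replace the sentence with wording such as: *A single composite avoids a multiplicity correction and may reduce Type II error for effects shared across tests; it can miss effects limited to few tests.*

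Add that the ESL minus carbamazepine composite difference is reported with a confidence interval at the level matching the primary test, and state that level. If the SD is 0.49 and n is 30, the expected half-width is about 0.18 at 95% or 0.25 at 99%. Add that a nonsignificant result excludes only differences outside that interval.

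No new per-test analysis is needed, because those comparisons are already planned.

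The cost is a change of SAP wording and one interval in the primary table. Design, sample size and conduct stay as they are. The downside for the sponsor is a less favourable reading of a null result.
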